6.2. Study endpoints

6.2.1. Primary Endpoints

6.2.1.1. Primary Effectiveness Endpoint

The primary effectiveness endpoint is the acute procedural success, defined as the proportion of subjects that achieve electrical isolation* of all PVs using FARAPULSE Pulsed Field Ablation system only.

** Electrical isolation of a PV is demonstrated by entrance block after a 20-minute waiting period if the subject is enrolled prospectively, otherwise the way to confirm electrical isolation should be recorded, including whether there is a waiting period and its duration. If exit block testing is performed, the PV will only be considered isolated if both entrance and exit block testing was successful.*

6.2.1.2. Primary Safety Endpoint

The primary safety endpoint is defined as the occurrence of the acute serious procedure-related and /or device-related adverse events at 7 days post index procedure based on the definitions contained in **Table 6.2-1.**

- Death
- Myocardial infarction
- Stroke/ TIA
- Peripheral or organ thromboembolism
- Cardiac tamponade / perforation
- Pulmonary edema
- Vascular access complications
- Heart block*
- Gastric motility/pyloric spasm disorders
- Pericarditis
- Atrial esophageal fistula
- Severe PV stenosis
- Phrenic nerve palsy

**Heart block not attributable to medication effect or vasovagal reaction.*

Table 6.2-1: Composite Safety Endpoint Definitions

Related SAE	Description/Criteria
Death	AE resulting in subject death

Related SAE	Description/Criteria
Myocardial infarction	
Defined as the presence of any one of the following criteria:
 
 • detection of ECG changes indicative of new ischemia (new ST- T wave changes or new LBBB) that persist for more than 1 hour • development of new pathological Q waves on an ECG • imaging evidence of new loss of viable myocardium or new regional wall motion abnormality
Phrenic nerve palsy	
Defined as absent phrenic nerve function as assessed by a change from baseline in the elevation of a hemidiaphragm, persisting beyond the end of the procedure that is:
 
 • Demonstrated radiographically by either an inspiration /expiration chest X-ray or fluoroscopic sniff test • Not due to a demonstrable pulmonary process such as atelectasis or pleural disease. 
Unresolved phrenic nerve palsy at 1-month follow-up visit will be involved in primary safety events. Phrenic nerve palsy will be evaluated at every follow-up visit thereafter and record the recovery time.
 
Persistent: Unresolved phrenic nerve palsy at 1-month follow-up visit will be reassessed during each follow-up visit. Unresolved phrenic nerve palsy at the 12-month follow-up visit will be considered as persistent phrenic nerve palsy

Stroke	
Rapid onset of a focal or global neurological deficit with at least one of the following:
 
 • Change in level of consciousness • Hemiplegia, hemiparesis, numbness or sensory loss affecting 1 side of the body • Dysphasia or aphasia • Hemianopia, amaurosis fugax, or • Other neurological signs or symptoms consistent with stroke 
The diagnosis of stroke requires that there be no other readily identifiable non-stroke cause for the clinical presentation (e.g., brain tumor, trauma, infection, hypoglycemia, peripheral lesion, pharmacological influences).
 
The duration of the defined neurological deficit(s) must be:
 
 • \geq 24-hours; OR • < 24-hours if 
 ○ Therapeutic intervention(s) were performed (e.g., thrombolytic therapy or intracranial angioplasty), OR ○ Available neuroimaging documents a new hemorrhage or infarct, OR ○ The neurological deficit results in death.

Related SAE	Description/Criteria
Transient ischemic attack	Defined as a new focal neurological deficit with: 
 • Symptom resolution within 24 hours • No new tissue injury demonstrated (if neuroimaging is obtained)
Peripheral or organ thromboembolism	A cardiac thrombus that occludes a more distal arterial site other than the central nervous system (see Stroke). Cutaneous petechiae are excluded from this definition.
Cardiac tamponade / perforation	The development of a pericardial effusion post-ablation that results in hemodynamic compromise, requires pericardiocentesis or results in a 1-cm or more pericardial effusion as documented by echocardiography. Cardiac tamponade/perforation should also be classified as “early” or “late” depending on whether it is diagnosed during or following initial discharge from the hospital.
Pericarditis	The development of pericardial inflammation post-ablation that results in an effusion that leads to hemodynamic compromise or requires pericardiocentesis, prolongs hospitalization by more than 48 hours, requires hospitalization, or persists for more than 30 days following the ablation procedure.
Pulmonary edema	Respiratory compromise resulting from cardiac dysfunction or volume overload leading to increased interstitial lung fluid requiring intubation or parenteral diuretics.
Vascular access complications	Vascular access complication (e.g., groin hematoma, AV fistula, pseudoaneurysm) requiring a significant and invasive intervention (e.g., surgical repair, blood transfusion or thrombin injection).
Heart block	Impairment of atrium-ventricular conduction that is related to a protocol-stipulated cardiac ablation procedure and that requires permanent pacing.
Gastric motility/pyloric spasm disorders	Evidence of impaired gastric motility or pyloric spasm that prolongs hospitalization, requires hospitalization or persists for more than 30 days.
Severe pulmonary vein stenosis	>70% reduction of an ablated measured PV diameter compared to the baseline CT/MRI scan, as determined by the CIL.
Atrio-esophageal fistula	Confirmation of a fistulous connection between the atrium and the lumen of the esophagus by radiographic, endoscopic or post-mortem examination

AV = atrioventricular, **CIL** = Cardiac Imaging Laboratory, **CT** = computed tomography, **ECG** = electrocardiographic, **LBBB** = left bundle branch block, **MRI** = magnetic resonance imaging, **PV** = pulmonary vein, **SAE** = serious adverse event.

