9.4.3. ATTEMPT

An ATTEMPT subject is one who signs informed consent, meets eligibility criteria, and has any study device inserted into the body but does not receive ablation (PFA energy) with the FARAPULSE Pulsed Field Ablation System for PVI. ATTEMPT subjects will be used for analysis of the primary and secondary safety endpoints and count toward the enrollment ceiling.

The original signed Informed Consent and any relevant documentation must be maintained in the site’s subject file. A subject ID will be assigned in the EDC system. ATTEMPT subjects are not allowed to be re-enrolled in the study.

Prospectively enrolled ATTEMPT subjects will be followed up to 30 days for safety. For

retrospectively enrolled ATTEMPT subjects, one-month follow-up data will be collected. ATTEMPT subjects will not need to complete data collection of the post-procedure arrhythmia. All applicable eCRFs, per the protocol, will be completed.

For ATTEMPT subjects, at the minimum the following forms must be completed:

- Enrollment and baseline forms such as, but not limited to: ICF, enrollment information and other related forms.
- End of Study form.
- Protocol Deviation form
- Adverse Event forms for any reportable event, as defined in Section 18.1 for any adverse event that occurs after signing the ICF, up to the point of subject withdrawal

9.4.4. *TREATMENT*

Any subject that signs the ICF, meets key eligibility criteria and has the specified study device inserted into the body and receives PFA ablation with the FARAPULSE Pulsed Field Ablation system will be classified as “TREATMENT”. The data collection of these subjects will be performed in accordance with the follow-up schedule and are included in all study analyses. A subject ID will be assigned in the EDC system.

All applicable eCRFs, per the protocol, must be completed for TREATMENT subjects. TREATMENT subjects do count towards the enrollment ceiling and will be used for analyses of the endpoints. The original signed ICF and any relevant documentation must be maintained in the center’s patient file.

9.5. *End-of-Study Definition*

A clinical trial is considered completed when the last participant’s last study data collection has occurred.

A subject is considered to have completed the study if he/she has completed all data collection including the last visit or assessment as shown in the Data Collection Schedule shown in **Table 10-1**.

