10.5.1.4. Additional ablations

CTI ablation: Ablation of the CTI may be performed using any approved catheter in subjects with a past history of CTI-mediated (typical) AFL, subjects who manifest typical AFL during a procedure or within the Blanking Period, or subjects who have inducible typical flutter. Bidirectional block should be demonstrated after the last CTI ablation. The CTI ablation data will be documented in the eCRF and does not constitute a Treatment Failure.

Other Ablation: Other ablation is not permitted under this protocol except when the Investigator determines that subject welfare requires ablation for an accessory pathway, AVNRT, treatment-emergent left AFL or incessant AT, using any approved ablation catheter. This decision and the associated ablation data will be documented in the eCRF and does not constitute an Effectiveness Failure.

If the subject presents with AF after all ablations are complete, cardioversion should be performed and will be noted. Cardioversions during the Index procedure do not signify procedural failures and are not to be reported as adverse events. Induction of or spontaneous conversion to AF during the procedure will not be considered an adverse event. If at any time during the ablation procedure the investigator is unable to continue the ablation with the designated investigational catheter (for the PV isolation), the investigator may consider the case a procedural failure and complete the case with a device determined best for the subject. The point at which failure was determined as well as the rationale must be documented. A protocol deviation will be documented in the EDC system.

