25.2. Definitions

Terms are defined in **Table 25.2-1**.

Table 25.2-1: Definitions

Term	Definition
Activated Coagulation/Clotting Time	ACT is a test that is used to monitor the effectiveness of high dose heparin therapy.
Acute Procedural Success	Achieve electrical isolation of all PVs using FARAPULSE Pulsed Field Ablation only.
Arterial-Venous Fistula	Abnormal communication between an artery and a vein.
Atrioesophageal Fistula	An atrioesophageal fistula is defined as a connection between the atrium and the lumen of the esophagus. Evidence supporting this diagnosis includes documentation of esophageal erosion combined with evidence of a fistulous connection to the atrium, such as air emboli, an embolic event, or direct observation at the time of surgical repair. A CT scan or MRI scan is the most common method of documentation of an atrioesophageal fistula.
Attempt Subject	Any subject that signs the consent form, meets eligibility criteria and has any study device inserted into the body but does not receive any PFA application with the study device.
AV block	A conduction disturbance that results in the partial inability of an electrical impulse generated in the atria to reach the ventricles. Refers to AV block not attributable to medication effect or vasovagal reaction.
Blanking Period	90-day period between ablation procedure and the initiation of the Long-term Effectiveness Evaluation Period during which subjects can be prescribed antiarrhythmic drugs as determined necessary by the investigator.
Cardiac tamponade / perforation	The development of a pericardial effusion post-ablation that results in hemodynamic compromise, requires pericardiocentesis or results in a 1-cm or more pericardial effusion as documented by echocardiography.

Table 25.2-1: Definitions

Term	Definition
	Cardiac tamponade/perforation should also be classified as “early” or “late” depending on whether it is diagnosed during or following initial discharge from the hospital.
Embolism	The sudden blocking of an artery by a clot or foreign material which has been brought to its site of lodgment by the blood current.
Enrolled Subject	A subject who is eligible for enrollment and signs an informed consent document to participate in the study.
Hematoma	A localized collection of blood, usually clotted, in an organ, space or tissue, due to a break in the wall of a blood vessel.

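### Cardiac tamponade/perforation is defined by an effusion that develops post-ablation, so a non-fatal effusion arising before any ablation does not meet the primary safety definition as written

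*Protocol*

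**What the plan says.** Protocol section 6.2.1.2 ties the primary safety endpoint to a table of definitions: "adverse events at 7 days post index procedure based on the definitions contained in" Table 6.2-1. The tamponade/perforation row of that table reads "The development of a pericardial effusion post-ablation that results in hemodynamic compromise, requires pericardiocentesis", with an effusion of at least 1 cm on echocardiography as the third alternative. The glossary in section 25.2 opens the same way: "The development of a pericardial effusion post-ablation that results in hemodynamic compromise". SAP section 3.2 lists the component by name and does not redefine it.

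Under section 9.4.3, an ATTEMPT subject "has any study device inserted into the body but does not receive ablation (PFA energy) with the FARAPULSE Pulsed Field Ablation System for PVI". The same section says "ATTEMPT subjects will be used for analysis of the primary and secondary safety endpoints and count toward the enrollment ceiling". Protocol section 11.2.1 and SAP sections 3.2.3 and 4.1 confirm that the safety set is ATTEMPT plus TREATMENT subjects, while effectiveness uses TREATMENT subjects only.

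Sections 5.3.2 and 10.5.1.1 give the order of the procedure: venous access, transseptal access with other approved devices, FARADRIVE sheath, FARAWAVE catheter, and only then ablation.

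**The concern.** The safety set admits subjects who may have had no ablation, but this component requires the effusion to come after ablation. Suppose an effusion arises during sheath or catheter placement and the case stops. The subject is ATTEMPT, enters the safety denominator, and has no qualifying tamponade event. The subject is also outside the effectiveness set, so a non-fatal event of this kind would appear in neither primary endpoint. A TREATMENT subject whose effusion arises before the first application is affected in the same way on the safety side.

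The secondary safety endpoint inherits the gap, because it reuses the primary events and adds only fistula, severe PV stenosis and persistent phrenic nerve palsy. With about 30 subjects intended to support registration (section 7.3), one event visibly changes the reported safety rate.

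**Working it through.** **1. What the timing word can mean.** The protocol does not define it, so its other uses have to be set side by side.

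- *After lesions are delivered.* Sections 5.2 and 10.5.1.1 contrast voltage mapping before and after ablation within one procedure. Section 10.5.2 collects post-ablation maps and diaphragm fluoroscopy at the procedure visit. Section 9.4.3 glosses ablation as PFA energy. On this meaning, an effusion before energy is excluded.
- *After the procedure.* Section 5.4.2 divides anticoagulation into before, during and after ablation, where the last means after the procedure. On this meaning, an effusion before energy is again excluded.
- *At any time from the start of the procedure.* No passage says this.

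**2. Whether another component catches a non-fatal case** (Table 6.2-1).

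- Pericarditis carries the same timing word.
- Vascular access complications are illustrated by access-site problems.
- Death has no such qualifier, but covers fatal cases only.

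None of these catches a non-fatal effusion before ablation.

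**3. Reproducing the plan's interval table.** The inputs are n = 30 and a two-sided 95% exact interval (protocol section 11.1.1.1.2; SAP section 3.2.2). For x events, the lower limit is the 0.025 quantile of Beta(x, n − x + 1) and the upper limit is the 0.975 quantile of Beta(x + 1, n − x). For x = 0 the upper limit reduces to 1 − 0.025^(1/30) = 11.57%.

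| Events | Rate | Computed 95% CI | Plan |
|---|---|---|---|
| 0 | 0% | 0 to 11.57% | 0 to 11.6% |
| 1 | 3.3% | 0.08 to 17.22% | 0.1 to 17.2% |
| 2 | 6.7% | 0.82 to 22.07% | 0.8 to 22.1% |
| 3 | 10.0% | 2.11 to 26.53% | 2.1 to 26.5% |

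The plan's table is correct.

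**4. Effect of one uncounted event.**

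- If there are no other events, 1/30 is reported as 0/30. The rate falls by 3.3 points and the upper limit by 17.22 − 11.57 = 5.65 points.
- If one other event is counted, 2/30 (0.8% to 22.1%) is reported as 1/30 (0.1% to 17.2%).

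**5. How likely this is.** The documents give no rate for effusions before energy. As pure assumption, with per-subject rate p, the chance of at least one in 30 is 1 − (1 − p)^30:

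- p = 0.5%: 14%
- p = 1%: 26%
- p = 2%: 45%

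These figures show only how the answer depends on p.

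**The case against.** The strongest objection is that the reading is too literal. The endpoint covers procedure- and device-related events, the component is named tamponade/perforation, and early versus late is set by hospital discharge, not by energy delivery. All this suggests that in-procedure events were meant to count. The inference about intent is fair, but the early/late note only sorts events that already meet the definition, and both meanings found elsewhere in the protocol exclude the case. Apparent intent is a reason to correct the wording.

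Second, nothing is lost to safety reporting: section 18.1 makes all adverse events and SAEs reportable, and section 20.1 has sponsor medical staff review them. That stands. The gap is in the composite rate. Other components, such as stroke/TIA and myocardial infarction, carry no such timing word and work normally for ATTEMPT subjects.

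A reader might also infer more than the documents support:

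- *That every tamponade in an ATTEMPT subject drops out.* ATTEMPT means no PFA energy for PVI, not no ablation. Section 10.5.1.4 lets the investigator "complete the case with a device determined best for the subject" and allows CTI ablation with any approved catheter. An effusion developing after either still qualifies, as does one that develops after ablation from an earlier perforation.
- *That ATTEMPT subjects were included specifically to capture device-insertion harm.* Section 9.4.3 states their inclusion, not its purpose.
- *That the pooled earlier data size the problem.* Two pericardial effusions in 121 subjects (section 4.1.3) would give 30 × 2/121 = 0.50 expected events and 1 − (1 − 2/121)^30 = 39%. But section 4.2 describes those subjects as ablated, and acute success was 40/40 and 81/81, so none was a case stopped before energy. One effusion was asymptomatic, with no statement that it met these criteria. The share arising before energy is not given.

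**Conclusion.** The point holds in a limited form. As written, Table 6.2-1 and section 25.2 exclude a non-fatal procedure- or device-related effusion that arises before any ablation, including one in an ATTEMPT subject who then receives none and is counted as event-free. This is a stated rule that would give a wrong count.

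The size is conditional: one such event separates 1/30 (3.3%, 0.1% to 17.2%) from 0/30 (0% to 11.6%). A reader might infer that the safety rate is already biased downward. The documents do not support that: it is understated only if such an event occurs and the wording is applied as it stands. No hypothesis test or success threshold is affected, because the plan has none.

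The conclusion assumes that the written definition governs classification, as section 6.2.1.2 says, and that 30 subjects are in the safety denominator.

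**What to change.** In Table 6.2-1 and section 25.2, replace the timing word in the tamponade/perforation row with: *during or after the index procedure, from initiation of venous access, whether or not PFA energy was delivered*. Review the same qualifier in the Table 6.2-1 pericarditis row. Have SAP section 3.2 refer to the amended definition, since it currently only lists the component.

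Venous access is the right anchor. Starting at first insertion of a study device would still miss an effusion at transseptal puncture, which precedes the sheath. The glossary already uses venous puncture to start total procedure time. The change does not reach INTENT subjects, who have no study device inserted and are outside the endpoint analyses under section 9.4.2.

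The cost is one phrase in two protocol tables and one cross-reference in the SAP, with no new data, since these events are already reportable. If analyses have been run, protocol section 11.3.7 and SAP section 5.5 provide for recording the change and its reason in the study report. The downside is that the safety rate may be slightly less favourable.

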6.2.2. Secondary Endpoints

6.2.2.1. Secondary Effectiveness Endpoints

1. Chronic Success: Proportion of subjects that free from effectiveness events defined as failure as below at 12 months post-procedure.

Effectiveness events determining a failure are defined as:

- Fail to achieve electrical isolation of all PVs using FARAPULSE Pulsed Field Ablation system only.
- After the Blanking Period (90 days post the procedure) to 12-month after the procedure:
 - 1) Occurrence of any Detectable AF, AFL* or AT captured by one of the following methods: ≥ 30 seconds in duration recording from 24-hour Holter Monitor or ≥ 10 seconds recording from 12-lead ECG, or
 - 2) Any cardioversion for AF, AFL* or AT, or
 - 3) Use of any Class I or Class III AADs[#] for the treatment of AF, AFL* or AT.
- At any time through 12 months after the procedure:
 - 1) Re-ablation for AF, AFL* or AT, or
 - 2) Use of amiodarone, except intra-procedurally to control an arrhythmia.
- 2. Proportion of PVs that achieve electrical isolation by using the FARAPULSE Pulsed Field Ablation system only.
- 3. Chronic success allowing AADs.

[#]It won't be considered as a failure if the subject has three-month visit happened after 90 days post the procedure, but still in the window (≤ 104 day) with AADs on, and physicians decide to take AADs off after this visit.

**excluding CTI-dependent flutter confirmed by EP study*

6.2.2.2. Secondary Safety Endpoints

Proportion of subjects that free from primary safety events defined as above through 7 days after the procedure and free from the following serious procedure-related and/or device-related adverse events at any time through the completion of 12-month follow-up visit. based on the definitions contained in **Table 6.2-1**.

- Atrial oesophageal fistula
- Severe PV stenosis
- Persistent phrenic nerve palsy*

**The study will collect information on phrenic nerve palsy observed before the end of the index procedure and, in case of occurrence, will track information for potential recovery during the study visits*

6.2.3. *Other Endpoints*

1. AF Symptom Assessment: AF symptoms will be assessed at baseline and 12 months.
2. Procedural parameters:
 - Total procedure time (initiation of venous access to venous access closure)
 - Left atrial dwell time (total time an ablation catheter is in the left atrium [LA])
 - Total PVI ablation time (first ablation to last ablation for PVI)
 - Fluoroscopy time (total duration of exposure)

[figure not shown]
7. Study Design

The REPLACE study is a retrospective and/or prospective single-center single-arm observational real-world study to observe the safety and effectiveness of the FARAPULSE Pulsed Field Ablation system for treatment of recurrent, symptomatic PAF in a Chinese population in the real world. Primary endpoints analysis is planned to be conducted after all enrolled subjects have completed data collection at 1-month follow-up visit. All the subjects underwent study device treatment will be followed up to 12 months after the procedure, and the secondary and other endpoints will be analyzed then. The final report will be completed then too.

7.1. *Scale and Duration*

Thirty ATTEMPT and TREATMENT subjects will be enrolled in this study. The enrollment period for this study is expected up to 6 months depending on the precent of patients enrolled prospectively. Each subject will be followed under standard of care after the ablation procedure with a follow-up duration of 12 months. The study duration is estimated up to 18 months. Primary endpoints analysis is planned to be conducted after all enrolled subjects have completed data collection at 1-month follow-up visit. All the subjects underwent study device treatment will be followed up to 12 months after the procedure, and the secondary and other endpoints will be analyzed then. The final report will be completed then too.

All the subjects will be enrolled from 1 site.

*The definitions of ATTEMPT and TREATMENT refer to Section 9.4.

Figure 7.1-1: REPLACE Study Design

